**Day 16+ / 24-Hour Follow-Up to Infusion 2:**

The procedures for this visit are identical to those described above for Day 2.

**Days 17-21+/ Phone Follow-Up:**

A study staff member will contact participants by telephone every other day after the 24-hour follow-up until day 21 of the study to track symptom trajectory using QIDS and MADRS. During these telephone follow-ups, subjects will also be asked about potential side effects or interaction effects they may be experiencing related to the study medications.

**Day 22+ / 7-Day Follow-Up to Infusion 2:**

The procedures for this visit are identical to those described above for Day 2. For special circumstances (e.g., inclement weather, transportation issues, considerable travel burden, etc.) this visit may occur over the phone. In the cases where a phone visit is required, we will forego the cognitive testing as there is not a way to administer this remotely, but all clinical measures and review of AEs will take place.

**Day 29+ / 14-Day Follow-Up to Infusion 2:**

The procedures for this visit are identical to those described above for Day 2. In addition, participants will be discharged from the study with appropriate referral. For special

circumstances (e.g., inclement weather, transportation issues, considerable travel burden, etc.) this visit may occur over the phone. In the cases where a phone visit is required, we will forego the cognitive testing as there is not a way to administer this remotely, but all clinical measures and review of AEs will take place.

***Day 43+ / 28-Day Telephone Call:***

A telephone call will be made to all subjects to inquire about any potential residual effects of ketamine or sirolimus and other AEs. Any additional follow-up and/or referrals will be arranged as clinically indicated.

**Phase Three Research Procedures:**

We anticipate recruiting and screening approximately 35 male and female Veterans and non-Veterans/civilians, between the ages of 21-65 years, in order to meet our target sample of 18 subjects. Screening, enrollment and discontinuation criteria are identical to Phase 1 and 2. Treatment and study procedures are identical to Phase 2, except that participants will have only 1 treatment day (i.e., Infusion 1) with open-label sirolimus+ketamine (i.e., no Infusion 2 of placebo+ketamine). The weekly follow-up post Infusion 1, will be up to Day 29+ (i.e., 4 weeks follow-ups instead of 2 weeks). The follow-up period was extended considering the prolonged antidepressant effects of the combined sirolimus+ketamine treatment. The collection, processing and analysis of peripheral inflammatory biomarkers will be completed under a separate protocol and consent (i.e., CA0008). Participants in Phase 2, who consented to be contacted for future studies, will be invited to participate in Phase 3. This approach will both facilitate recruitment and reduce study risk as these participants who already received and well tolerated the study drug.

***Ketamine Administration:***

Subjects will complete two test days separated by at least two weeks. Subjects will receive an infusion of ketamine (0.5 mg/kg infusion over approximately 40 minutes). All subjects will receive two ketamine infusions—once with a placebo and once with a single dose of sirolimus (6 mg, oral administration). The order of placebo and sirolimus is randomized. Note, the ketamine dose and route of administration are similar to that seen in previous investigations and has demonstrated high safety and tolerability.

A physician who is trained and has significant experience with both ketamine and infusion studies will oversee and administer the ketamine infusions. A nurse will accompany the subject throughout the study sessions, from the insertion of bilateral cannula for drug infusion and blood sampling, through to recovery following ketamine infusion.

***Sirolimus or Placebo Dosing:***

Subjects will receive a single 6 mg oral dose via oral solution of sirolimus or a dose of placebo approximately two hours prior to the infusions. As above, the order of placebo and sirolimus is randomized. The sirolimus dose as well as the placebo solution will be given in 2 ounces of orange juice, followed by 4 oz of water. As for the tolerability of single dose of sirolimus, based on data in healthy subjects and consultation with [name], Director of Transplant Medicine, Yale University, an expert with sirolimus treatment, it is expected that a single 6 mg oral dose will produce minimal adverse effects.

### ***Screening Measures:***

Assessments that will be used during the psychological evaluation are listed below.

### **Psychological Evaluation:**

1. *Alcohol and Consumption Habits:* This is a brief measure that documents alcohol, caffeine, and nicotine habits.
2. *Beck Suicide Ideation Scale (BSI):* The BSI is a 21-item self-report questionnaire that may be used to identify the presence and severity of suicidal ideation. Items on this measure also assess the respondent's suicidal plans, deterrents to suicide, and the level of openness to revealing suicidal thoughts.
3. *Behavioral Inhibition & Activation Scales (BIS/BAS):* The BIS/BAS is a self-report scale designed to assess dispositional sensitivity to the behavioral inhibition system (BIS) and the behavioral activation or behavioral approach system (BAS).
4. *Big Five Inventory (BFI):* The BFI measures an individual on the Big Five Factors (dimensions) of personality (Goldberg, 1993). Each of the factors is then further divided into personality facets.
5. *Brief TBI Screen:* The Brief Traumatic Brain Injury Screen, also called the DVBIC TBI Screening Tool, is a 3-item instrument used to evaluate the presence of head injury and related symptomatology. It was validated in a small, initial study conducted with active duty service members who served in Iraq/Afghanistan between January 2004 and January 2005.
6. *Clinical Global Impressions Scale (CGI) and the Patient Global Impressions Scale (PGI):* The CGI and PGI are widely used instruments, which assess overall severity of illness on a 1 to 7 point scale with 1 indicating "normal, not at all ill" and 7 indicating "among the most extremely ill patients." These instruments also assess global improvement on a 1-to-7 point scale with 1 indicating "very much improved," 4 indicating "no change" and 7 indicating "very much worse."
7. *Clinician Administered Dissociative States Scale (CADSS):* The CADSS has self and interviewer-administered items including 5 subscales, generated a priori, evaluating dissociation including altered environmental perception, time perception, spatial/body perception, derealization and memory impairment.
8. *Cognitive tasks:* This will include CogState, a well-validated short computerized cognitive tasks. These short computerized tasks along with a brief neuropsychological battery will assess cognitive functions.
9. *Columbia-Suicide Severity Rating Scale (C-SSRS):* The C-SSRS is a brief clinician administered and standardized measure that uniquely assesses essential information about suicide behavior, ideation, lethality and severity, and distinguishes between suicidal occurrences and non-suicidal self-injury.
10. *Early Trauma Inventory (ETI-SR):* The ETI-SR is a self-report instrument to assess childhood trauma and includes physical, emotional and sexual abuse as well as general traumas.
11. *Global Perceived Early Life Stress (GPELS):* The GPELS is a self-report of perceived stress during childhood.
12. *Hamilton Anxiety Rating Scale (HAM-A):* The HAM-A is a standardized clinician-rated instrument to evaluate the severity of anxiety symptoms.
13. *Klein Loss Scale (KLS):* The KLS is a self-report of parental loss or separation during childhood.

14. *Life Events Checklist (LEC)*: The LEC is a self-report instrument that measures reports of traumatic life events.
15. *Perceived Stress Scale (PSS)*: This is a 10-item self-report questionnaire to assess the severity of perceived stress over the past month.
16. *Cumulative Adversity Interview (CAI)*: A multifaceted semi-structured assessment of stressful life events and chronic subjective stress used in research on stress and psychopathology.
17. *Massachusetts General Hospital Antidepressant Treatment History Questionnaire (MGH-ATRQ)*-This is a self-rated questionnaire used to determine treatment resistance in major depressive disorder.
18. *Montgomery-Asberg Depression Rating Scale (MADRS)*: The MADRS is a standardized instrument to ascertain depressed mood and neurovegetative signs and symptoms of depression.
19. *Penn State Worry Questionnaire (PSWQ)*: The PSWQ is a self-report questionnaire to assess for 'worry' symptoms that are typical of generalized anxiety.
20. *Pittsburgh Sleep Quality Index (PSQI)*: The PSQI is a self-report questionnaire to assess sleep quality and sleep disturbance.
21. *Positive and Negative Symptom Scale (PANSS)*: The PANSS is commonly used to measure the severity of symptoms in psychotic disorders. It is a clinician- administered scale and includes three categories of symptoms: (1) positive symptoms, such as hallucination and delusion; (2) negative symptoms, such as flat affect and difficulty in abstract thinking; (3) general psychopathology, such as mannerisms and posturing.
22. *PTSD Checklist (PCL)*: The PCL is used to measure PTSD symptoms and is a self-report questionnaire that has high reliability.
23. *Quick Inventory of Depressive Symptoms – Self-Report (QIDS-SR)*: The QIDS-SR is a patient-rated depression instrument.
24. *Sheehan Disability Scale (SDS)*: The SDS is a brief self-rated measure of disability and impairment.
25. *Systematic Assessment for Treatment Emergent Events (SAFTEE)*: The SAFTEE is a commonly used instrument originally developed by NIMH and adapted into a self-report instrument. It examines, in systematic fashion, possible treatment-emergent side effects and probes for specific adverse symptoms, including suicidal thoughts and behaviors, and self-injurious behavior.
26. The Mini International Neuropsychiatric Interview (MINI) will be used to provide current and past diagnoses of psychiatric disorders, notably the inclusion/exclusion criteria of a current major depressive episode.
27. *Socio-demographic/General Information*: At intake, demographic data and medical history will be assessed with interviews and self-report forms that provide data on age, race, socioeconomic status, marital status, educational and occupational levels, and significant medical history. These are adapted from previous diagnostic and clinical studies at this center.

**Medical Assessments:**

1. Physical exam by a licensed physician, or Advanced Practice Registered Nurses (APRN's).
2. Routine laboratory studies including a complete blood count (CBC) w/ differential, a comprehensive metabolic panel, HCG, TSH, fT4, CRP, and ESR, in addition to urinalysis and urine toxicology screen. Additional tests will be requested as clinically indicated.

3. Urine toxicology screens will be performed at the screening appointment and will be administered more frequently if the clinician or research staff becomes concerned about possible illicit drug use. Patients will be informed of random urine drug screens.
4. An ECG will be performed.
5. Pregnancy Tests- female subjects will have a blood sample drawn for a pregnancy test.

### *Audio Recording:*

Clinician administered interviews may be audio recorded for inter-rater reliability and staff training purposes. Subject identifying information will not be on the audio recording. Recordings will be stored in a locked cabinet when not in use. Subjects will be asked on the consent form to indicate whether or not they agree to having their clinical interviews audio recorded. If subjects disagree to having their clinical interview audio recorded, it will not affect their eligibility to participate in study procedures.

### *Data Storage:*

Data will be housed at VACHS West Haven campus in Building 1, where the PI's office is located. The computers where data will be stored are password protected and behind the VA firewall. Only approved research staff will have access to the screening data.

**Table 2. Schedule of Study Events**

MADRS	x	x	x	x	x	x	x	x	
M-MACE	x								
MGH-ATRQ	x								
Medical Evaluation	x								
PANSS		x			x				
PCL	x	x	x	x	x	x	x	x	
PSQI	x	x	x	x	x	x	x	x	
PSWQ	x	x	x	x	x	x	x	x	
QIDS-SR	x	x	x	x	x	x	x	x	
Sirolimus/Placebo Dose		x			x				
SAFTEE	x	x	x	x	x	x	x	x	x
MINI	x								
SDS	x								
Serum Pregnancy	x								
Urinalysis	x	x			x				
Urine		x			x				
Toxicology/Pregnancy									
Vital Signs	x	x			x				

\*Informed consent will be obtained prior to any study procedure.

**Abbreviations:** Big Five Inventory (BFI), Behavioral Inhibition & Activation Scales (BIS/BAS), Beck Suicide Inventory (BSI), Brief TBI Screen (B-TBI-S), Clinician Administered Dissociative States Scale (CADSS), Clinical Global Impression Severity/Improvement (CGI-S/I), Patient Global Impression-Severity/Improvement (PGI-S/I), Cogstate and brief neuropsychological battery comprises the cognitive testing portion, Columbia-Suicide Severity Rating Scale (C-SSRS), electrocardiogram (ECG), Early Trauma Inventory – Self Report (ETI-SR), Global Perceived Early-Life Stress (GPELS), Hamilton Anxiety Rating Scale (HAM-A), Klein Loss Scale (KLS), Life Events Checklist (LEC), Montgomery-Asberg Depression Rating Scale (MADRS), Modified Military Acute Concussion Evaluation (M-MACE), MGH Antidepressant Treatment Response Questionnaire (MGH-ATRP), Positive and Negative Symptom Scale (PANSS), Pittsburgh Sleep Quality Index (PSQI), Penn State Worry Questionnaire (PSWQ), Quick Inventory of Depressive Symptomatology – Self Report (QIDS-SR), Systematic Assessment for Treatment Emergent Events (SAFTEE), Structured Clinical Interview for DSM (SCID), Sheehan Disability Scale (SDS). \*\*Phone call follow-ups will be conducted every other day for five days following both infusion days.

### ***Criteria for Discontinuation***

Participants may be discontinued from this proposed study at any time. Specific reasons for discontinuing a participant include:

- Voluntary discontinuation by the participant, who is at any time free to discontinue his/her participation in the study without prejudice to further treatment.
- Clinical deterioration: The following are objective criteria for clinical deterioration, (1) a 25% increase in MADRS scores at any time during the study, and (2) the onset of active suicidality as assessed by the study physicians or by scoring 5 or more on the item-10 of MADRS.
- Stopping birth control or positive pregnancy test.

- Safety reasons as judged by the investigator.
- Severe non-compliance to protocol as judged by the investigator.
- Incorrect enrollment i.e., the subject does not meet the required inclusion/exclusion criteria for the study.

A subject that discontinues will always be asked about the reason(s) for discontinuation and the presence of any adverse events. If possible, they will be seen and assessed by the investigator. Adverse events will be followed up as medically necessary.

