***Exclusion Criteria:***

1. Subjects with a diagnostic history of schizophrenia or schizoaffective disorder, or currently exhibiting manic or mixed episodes or psychotic features as confirmed by the Mini International Neuropsychiatric Inventory.
2. Current, ongoing serious suicidal risk as assessed by evaluating investigator or by scoring 5 or more on the item-10 of the MADRS.
3. Patients with unstable or inadequately controlled medical conditions.
4. Patient requiring prohibited medication (see Table 1).
5. Patient with history of organ transplant.
6. Meet criteria for a diagnosis of substance dependence (amphetamines, cocaine, hallucinogens, inhalants, opioids, sedatives/hypnotics/anxiolytics) within the three months prior to screening date.
7. Positive urine drug screen for cannabis, cocaine, PCP, or barbiturates.
8. Positive pregnancy test at screening at any screen given during the study.
9. Known sensitivity to sirolimus or ketamine.
10. History of sensitivity to heparin or heparin-induced thrombocytopenia.
11. Resting blood pressure lower than 85/55 or higher than 150/95, or resting heart rate lower than 45/min or higher than 100/min.

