***Privacy:***

All reports generated from the data obtained through this study will protect the confidentiality of the subjects who participate in this study. In case of a medical emergency, the medication group blinding can be broken by the principal investigator or a designated covering staff member, in order to supply information required for emergency medical care of research subjects. All subjects will be given a “wallet card” which identifies them as a study participant and lists the emergency contact numbers. If a subject shows clinical deterioration (worsening of depressive symptoms that is higher than 25% of baseline MADRS scores), the participant will exit the study and a study psychiatrist (or APRN) will determine whether a higher level of care (e.g. referral to treating psychiatrist or referral to emergency or inpatient care) is needed.

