#### **Day 0-Baseline Screening:**

Individuals deemed eligible after the telephone pre-screening will undergo a full in-person screening appointment at the VA Connecticut Healthcare System (VACHS), West Haven campus. During the evaluation, the study procedures will be described and the subject's questions will be answered prior to obtaining an informed consent. The investigator or research staff member obtaining consent will ask the participant to provide a brief summary of the study to ensure they understand what is being asked of them and any potential risks and benefits. Once consent is obtained, subjects will participate in the following procedures: a biopsychosocial interview, psychological evaluation, a brief cognitive evaluation, a physical examination, ECG, breathalyzer and a blood sample

Figure 3. Phase 2 study design.

for routine testing. A urine sample will be collected for urine toxicology, pregnancy, and urinalysis.

In addition, because this is a clinical trial for medications for increased safety pre-cautions, female subjects of childbearing age will have a blood sample drawn for a pregnancy test. If a female subject is pregnant, breast-feeding, intending to become pregnant, or does not agree to use an approved birth control method (i.e., oral, injectable, or implant birth control, condom, diaphragm with spermicide, intrauterine device, tubal ligation, abstinence, or partner with vasectomy) she will be excluded.

After completing the baseline screening and being deemed eligible for participation in the study, subjects will be randomized to one of two conditions at Time/Infusion 1 — ketamine+sirolimus (with placebo at Time 2) or ketamine+placebo (with sirolimus dose at Time 2).

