#### ***Day 1 / Infusion 1:***

First, the MADRS assessment will be completed to confirm that the participant continues to have significant depressive symptoms (i.e. MADRS  $\geq 18$ ) prior to proceeding with Infusion 1. Participants will be rescheduled if depression severity was not met‡. If depression severity is confirmed, Infusion 1 procedures will be completed as follows:

- Subjects will present to the VACHS to complete vitals and provide a urine sample for drug and pregnancy testing.
- Subjects will receive a single 6 mg oral dose of sirolimus or placebo, dependent on their randomization. They will be monitored for any acute allergic reaction or other adverse event. Clinical assessments will be administered throughout the infusion visit, including PSWQ, PSQI, MADRS, QIDS-SR, SAFTEE, CGI, HAM-A, CADSS, PANSS\*\* (assessment measures are described below).
- Intravenous lines will be placed.
- A blood draw for sirolimus level will occur prior to the beginning of the ketamine infusion.
- Ketamine 0.5 mg/kg will be infused over approximately 40 minutes. Subjects will be monitored closely by study physician and nurse.
- A blood draw for ketamine will occur during the ketamine infusion.
- One additional blood draw for sirolimus will occur shortly before the participants are discharged from their study visit.
- Subjects may be discharged home after being cleared by a study physician.

‡ Screening procedures will be repeated if participant was not randomized within 60 days of screening. \*Blood pressure, heart rate, and oxygen saturation will be recorded every 10 minutes during infusion (T0-40 minutes). \*\* Items that could not change within a session, e.g. sleep and appetite, will be carried forward from the initial ratings.

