- 4) We will review the test day with the subject to deal with their feelings and reactions to each test day before they leave.
- 5) We will ask the subject to contact us at any time if any unpleasant effects occur.
- 6) We will ask the subject not to engage in demanding work in the day following the test sessions and we will work with the subject to schedule your test days accordingly.
- 7) If the subject has any lingering medication effects, such as sedation, we will terminate the remaining test days and work with him/her until these side effects have resolved.
- 8) If the subject develops psychiatric symptoms, we may admit him/her to the hospital. This may be involuntary if he/her are in danger of harming self or others.
- 9) We will conduct 24-hour, 7-day, 14-day, and 28-day follow-up assessments for residual effects.

**Clinical Deterioration:** Subjects will be closely monitored with serial depression rating scales. In the event of clinical deterioration, the subject will be discharged from the study protocols and the study physicians will initiate treatment as clinically recommended. As noted above, the following are objective criteria for acute decompensation: (1) a 25% increase in MADRS scores at any time during the study, or (2) the onset of active suicidality as assessed by the study physicians or by scoring 5 or more on the item-10 of MADRS. Study participants will be informed that a decision to initiate standardized psychotropic and/or psychotherapeutic regimens will not adversely affect their ability to participate in future protocols or receive treatment at VACHS, Yale Depression Research Program (YDRP), CMHC, or private psychiatric practice in the community. All participants will be treated by a study physician until appropriate referral is arranged.

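### The two criteria for clinical deterioration are joined by *and* under Criteria for Discontinuation but by *or* where Minimizing Risks restates them

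*Combined protocol and SAP*

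**What the plan says.** Three places in the combined protocol and SAP describe when a worsening participant leaves the study.

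- Criteria for Discontinuation introduces objective criteria for clinical deterioration and lists them as "1) a 25% increase in MADRS scores at any time during the study, and (2) the onset of active suicidality". Suicidality is judged by the study physicians or by a score of 5 or more on MADRS item 10. A separate bullet in the same list reads "Safety reasons as judged by the investigator".
- Minimizing Risks, under Clinical Deterioration, says it is repeating what was noted above, and gives the pair as "1) a 25% increase in MADRS scores at any time during the study, or (2) the onset of active suicidality". The definition of suicidality is the same.
- The Privacy section states a rule on MADRS alone: "worsening of depressive symptoms that is higher than 25% of baseline MADRS scores), the participant will exit the study".

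Phase Three Research Procedures makes the discontinuation criteria for that phase identical to those of Phases 1 and 2. The target there is 18 participants.

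**The concern.** This is the study's objective withdrawal rule for safety, and it should read the same wherever staff look it up. One section can be taken to require both signs. The section that claims to repeat it requires either. A participant whose MADRS rises without suicidality, or who becomes suicidal without the MADRS rise, could therefore be classified differently according to which page is open.

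The section most likely to be consulted on withdrawal is the one headed Criteria for Discontinuation, and that is the one with *and*. The text that makes MADRS worsening sufficient by itself sits under Privacy, where few would look for it.

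The Background already reports results of Phases 1 and 2, so the wording matters now for Phase Three, which inherits it.

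**Working it through.** No figure in the plan has to be reproduced. The check is to set the three texts side by side and run through the possible cases.

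**Inputs.** Criterion 1 is the 25% MADRS rise; criterion 2 is active suicidality. For the comparison, take a rise of more than 25% from baseline, so that criterion 1 is satisfied however each section words it.

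| MADRS rise | Suicidality | Criteria for Discontinuation, read literally | Minimizing Risks | Privacy |
|---|---|---|---|---|
| no | no | not met | not met | not met |
| yes | no | not met | met | met |
| no | yes | not met | met | not addressed |
| yes | yes | met | met | met |

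**Result, literal reading.** Criteria for Discontinuation is met in 1 of the 4 combinations and Minimizing Risks in 3 of 4. They disagree in 3 − 1 = 2 combinations, the two in which only one sign is present. In the MADRS-only case the Privacy section sides with Minimizing Risks. These are counts of logical cases, not proportions of participants.

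**Result, list reading.** If *and* only closes a list of criteria that are each sufficient, Criteria for Discontinuation is met in the same 3 combinations as Minimizing Risks, and the disagreement disappears.

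**Which reading the documents favour.** Three features point to the list reading:

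- Minimizing Risks describes itself as a repetition and uses *or*.
- Privacy treats the MADRS criterion as sufficient alone.
- At entry, suicidality is a ground by itself: "Current, ongoing serious suicidal risk as assessed by evaluating investigator or by scoring 5 or more on the item-10 of the MADRS".

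One feature points the other way. Within the same bullet, Criteria for Discontinuation uses *or* for the two ways of establishing suicidality, so a careful reader may suppose that *and* between the two criteria was meant as *and*.

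**Reference score.** Privacy measures the change from baseline. The other two sections name no reference and do not name a different one.

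**The case against.** The strongest reply is that the documents already answer the question. The bullet introduces criteria in the plural and ends the list with *and*; it does not say that both must be met. The restatement says *or*, and the Privacy rule works on MADRS alone. Only one word, taken literally and in isolation, supports the requirement for both. Most of this stands, and it is why the point is minor. It does not remove the mismatch: the reader has to find two other sections to learn what the principal one means.

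Three stronger readings are tempting, and the documents do not support them.

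- A reader might infer that the protocol keeps a suicidal participant in the study unless the MADRS has also risen. It does not. The discontinuation list is not exhaustive, it allows withdrawal at any time, and it includes the investigator's safety ground. No section requires a deteriorating participant to continue.
- A reader might infer that the sections contradict each other on what the 25% is measured from. Silence in two places and baseline in a third are compatible. One may ask whether baseline is the score from the visit headed "Day 0-Baseline Screening" or the score from the Day 1 check, of which the plan says "First, the MADRS assessment will be completed to confirm that the participant continues to have significant depressive symptoms". That is a missing detail and not a contradiction. Nor does any section suggest counting the rise from a participant's lowest score, and the Privacy wording speaks against it.
- A reader might infer a bias in the MADRS analysis through differential withdrawal. Nothing in the documents shows that anyone was or would be classified differently in practice, so no such effect is claimed.

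**Conclusion.** The inconsistency is real but minor. Two sections that purport to state the same rule join its two criteria differently, and a third gives one criterion as sufficient alone. Read literally, the sections part company for participants with exactly one sign. Read as a list, they agree, and the balance of the text favours that reading.

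The conclusion rests on the wording alone and needs no assumed scores. How many of the 18 planned Phase Three participants might show only one sign cannot be estimated from the documents. The practical effect is limited by the investigator's safety ground. The case for acting is that a safety-withdrawal rule should not depend on how one conjunction is read, and that correcting it needs only a wording change.

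**What to change.** Reconcile the Privacy section, Criteria for Discontinuation and the Clinical Deterioration paragraph of Minimizing Risks so that the link between the MADRS criterion and the suicidality criterion is the same in each. While doing so, carry the Privacy section's reference to baseline into the other two. Confirm that the reconciled text is the one Phase Three Research Procedures adopts.

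Which rule is clinically right is for the investigators to decide; the request is only that the sections agree. The cost is a wording amendment, with no new procedures or data.
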